2.2 CHARACTERISATION OF SEROLOGICAL MARKERS OF SARS-COV-2 INFECTION (TASK 6.3)

This task will characterize the host antibody responses with quantitative serology (anti-S and anti-N) on Abbott, Roche, MesoScale Discovery (MSD), or similar platforms as well as (pseudo-) seroneutralisation assays. These assays will be performed on populations with various degrees of COVID-19 severity and vaccinated individuals, also with breakthrough infections.

2.3 CHARACTERISATION OF CELLULAR IMMUNITY FOR SARS-COV-2 INFECTION (TASK 6.4)

Vaccinated and non-vaccinated COVID-19 patients with varying degrees of disease severity and SARS-CoV-2-positive non-symptomatic individuals will be studied for the balance and the phenotypes of T and B cells as a function of disease course and severity as well as response to vaccination. This task will chiefly employ flow cytometric analyses with CD45, CD3, CD4, CD19, FOXP3, Ki-67, CD38 markers, viability and IFN γ release assays.

2.4 CYTOKINOME ANALYSIS (TASK 6.5)

Vaccinated and non-vaccinated COVID-19 patients with varying degrees of disease severity, SARS-CoV-2-positive non-symptomatic individuals and vaccinated individuals will be studied on MSD panels, Luminex panels and on select ELISAs. As an outcome, panels of cytokine markers predicting disease severity, mortality, breakthrough infections, and long term sequelae will be generated.

2.5 NEXT GENERATION SEQUENCING (NGS) OF COVID-19 COHORTS (TASK 6.6)

In-depth human genetic analysis will be conducted using WGS or whole exome sequencing (WES) followed by functional analyses of the most promising variants. Additionally, serum samples will be utilized for detection of auto-antibodies against type I interferons (IFNs).

2.6 EPIGENOME-WIDE ANALYSES (TASK 6.7)

Genome-wide methylation analyses of COVID-19-positive patients in addition to a small number of control patients will enable differentiation of inherited and acquired genomic regulatory features through COVID-19 infection, which result in severe disease or an efficient clearing of infection through immune responses.

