11. STUDY PROCEDURES

In Figure 1, a study work flow is shown.

Figure 1: study work flow

All included patients will be evaluated during the scheduled visits for the underlying condition. During such visits, the following actions are required:

- Distribution of a questionnaire to capture the impact of COVID-19 pandemic on the socio-economic indicators, on the access to health care services, and to investigate risk perception and behavior towards preventing infection and COVID-19 disease, including vaccine acceptance. This questionnaire should be administered at two different time-points with an interval of at least 6 months to capture changes in behavior over the study period (Annex 1a or Annex 1b in case of children cohorts).

- Distribution of psychological scale questionnaires to investigate the impact of lockdown measures on mental health (Annex 2).
- Screening for past and/or current COVID-19 disease by medical interview, serology determination and nasopharyngeal swab or saliva specimens' collection.
- Collection, processing and storage of plasma for cytokine and chemokine analysis.
- Collection, processing and storage of serum for the subsequent sero-neutralization and type I IFNs autoantibodies detection.
- Collection, processing and storage of PBMCs for the subsequent anti-COVID-19 cellular immunity analysis.
- Collection, processing and storage of whole blood for genetic and epigenetic analysis.
- Collection, processing and storage of nasopharyngeal samples for SARS-CoV-2 detection and variant identification if clinically relevant.
- Collection, processing and storage of stool samples for metagenomic sequencing.
- In immunocompromised fragile cohorts, laboratory tests to assess the baseline “net state of immunosuppression” including whole blood count, lymphocyte differentiation, immunoglobulin levels, and complement (C3) levels should be done at the baseline (first clinical evaluation).

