3.1.1 Sample collection and management

Sampling is required to be performed on the day of diagnosis and at following timepoints as shown in Table 2. Patient inclusion will primarily be based on availability of informed consent for the outlined tasks as well as availability of multiple samples per patient. Informed consent forms should clearly request permission to perform human genetic and epigenetic analyses, without which these analyses cannot be undertaken.

Table 2. Overview sampling and data collection in ORCHESTRA cohorts in COVID-19 patients including long-term sequelae.

| | D0 ¹ | 3 months ¹ ±1 month | 6 months ¹ ±1 month | 12 months ¹ ±1 month | 18 months ¹ ±2 month | Objective |
|---|-----------------|-----------------------------------|-----------------------------------|------------------------------------|------------------------------------|--|
| NP swab | x | x ^{2,3} | x ^{2,3} | x ^{2,3} | x ² | Viral variant and metagenomic sequencing |
| 2 x 2 mL serum tube (serum) | x | x | x | x | x | Immune - serology and type I IFNs autoantibodies |
| 4 mL EDTA blood tube (plasma) | x | x ⁴ | x ⁴ | x ⁴ | x ² | Immune - cytokine and chemokine |
| 1 (if possible 2) 9 mL heparin tube (PBMCs) | x | x ⁴ | x ⁴ | x ⁴ | x ² | Immune - cellular |
| 2 x 2 mL EDTA tube (whole blood) | x | x | x | x | x | Genetic and epigenetic analyses |
| Stool sample (faeces or rectal swab) | x | | x | | x | Metagenomic sequencing |

1. Day 0: first positive SARS-CoV-2 PCR test. Follow-up of 3, 6, 12, and 18 months start from Day 0.
2. Reassessed only if outside the normal ranges at the previous assessment or if clinically indicated.
3. At least one of the three timepoints (month 3, month 6, month 12) is required to perform metagenomic analyses.
4. At least one of the three timepoints (month 3, month 6, month 12) is required.

| | |
|----------|--|
| Level I | Assessments of Level I are mandatory |
| Level II | Customized according to the feasibility of each cohort |

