3.2 SAMPLING TIMEPOINTS FOR VACCINATED INDIVIDUALS

3.2.1 Sample collection and management

Vaccinated individuals in WP4 and WP5 will be sampled according to the time points outlined in Table 3. In case of breakthrough infections post vaccination, samples will be collected as outlined in Table 2. Vaccination is (mostly) performed in two doses. Collection is to be performed prior to administration of dose 1 and dose 2, and 3, 6, and 12 months after the first dose (Table 3). Patient inclusion will primarily be based on availability of informed consent for the outlined tasks as well as availability of multiple samples per patient. Informed consent forms should clearly request permission to perform human genetic and epigenetic analyses, without which these analyses cannot be undertaken.

Table 3. Overview sampling and data collection in ORCHESTRA cohorts for vaccinated individuals.

| | 1 st dose | 2 nd dose ¹ | 3 months ² (± 1 month) | 6 months ² (± 2 months) | 12 months ² (± 3 months) | Objective |
|---|----------------------|-----------------------------------|--------------------------------------|---------------------------------------|--|--|
| NP swab | x ³ | x ³ | x ⁴ | x ⁴ | x ⁴ | Viral variant and metagenomic sequencing |
| 2 x 2 mL serum tube (serum) | x | x | x | x | x | Immune - serology and type I IFNs autoantibodies |
| 4 mL EDTA blood tube (plasma) | x | x ⁵ | x ⁵ | x ⁵ | x ⁵ | Immune - cytokine and chemokine |
| 1 (if possible 2) 9 mL heparin tube (PBMCs) | x | x ⁵ | x ⁵ | x ⁵ | x ⁵ | Immune - cellular |
| 2 x 2 mL EDTA tube (whole blood) | x | | x | x | x | Genetic and epigenetic analyses |
| Stool sample (faeces or rectal swab) | x | | x | | | Metagenomic sequencing |

1. The assessment at 2nd dose is mandatory in patients who will receive such dose within 8-12 weeks after first dose (current AstraZeneca vaccination schedule).
2. 3, 6, and 12 months counted from 1st dose.
3. At least one timepoint at 1st or 2nd dose is required.
4. At least one of the three timepoints (month 3, month 6, month 12) is required.
5. At least one of the four timepoints (2nd dose, month 3, month 6, month 12) is required.

| | |
|----------|--|
| Level I | Assessments of Level I are mandatory |
| Level II | Customized according to the feasibility of each cohort |

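### Task 6.7 says infected patients plus a few controls will separate inherited from infection-acquired methylation, but that comparison cannot tell acquired marks from pre-existing ones, and the claim is not tied to the pre-infection blood already scheduled

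*Protocol*

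**What the plan says.** Annex 4, section 2.6 (Task 6.7) says that methylation analysis of COVID-19-positive patients "in addition to a small number of control patients will enable differentiation of inherited and acquired genomic regulatory features through COVID-19 infection". It links those features to disease course: "which result in severe disease or an efficient clearing of infection through immune responses". It gives no number of cases or controls, no matching, and no infection or vaccination status for the controls.

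Three other parts of the protocol bear on the claim.

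- **COVID-19 patients.** Annex 4 Table 2 takes EDTA whole blood for genetic and epigenetic analyses at Day 0 and months 3, 6, 12 and 18. Its footnote fixes the origin: "Day 0: first positive SARS-CoV-2 PCR test".
- **All included patients.** Section 11 of the protocol lists among the actions at visits for the underlying condition: "Collection, processing and storage of whole blood for genetic and epigenetic analysis". Section 8 says that the cohorts include people with and without SARS-CoV-2 infection.
- **Vaccinated patients.** Annex 4, section 3.2.1 says "Collection is to be performed prior to administration of dose 1 and dose 2, and 3, 6, and 12 months after the first dose". Within that schedule, Table 3 marks whole blood at dose 1 and months 3, 6 and 12, but not at dose 2. Breakthrough infections then move to the Table 2 schedule.

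Task 6.6 (Annex 4, section 2.5) adds whole-genome or whole-exome sequencing. Annex 4 Table 1 assigns the same blood sample type to Tasks 6.6 and 6.7.

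**The concern.** To say that a feature was acquired through infection is to say that infection changed it. Comparing infected patients with controls asks something else: whether the two groups differ now. They may differ because infection changed a site, because genotype differs, or because the groups already differed in disease, treatment, age or cell composition. Here the last is a serious possibility. The cohorts span transplant, HIV, cancer, autoimmune disease, Parkinson disease, pregnancy and childhood, and section 2.6 does not say from which of these the controls come.

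At stake is the validity of a stated conclusion. Epigenetic characterisation is a listed objective (Section 7). A mark of the fragile condition or its therapy could not be told apart from an effect of COVID-19, and a pre-existing difference in the opposite direction could hide a real effect. The number of controls is not the root of the problem. A larger control group estimates the same ambiguous difference more precisely.

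**Working it through.** The protocol gives no sample size, effect size or power for Task 6.7, so there is no figure to reproduce. The check has two parts.

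**1. What each planned data source can identify**

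| Source | Separates inherited from non-inherited? | Separates pre-existing from acquired through infection? |
|---|---|---|
| Infected versus controls (section 2.6) | No | No |
| Day 0 and months 3 to 18 in infected patients (Table 2) | No | No, for a shift already present at Day 0 that persists |
| Sequencing (Task 6.6) | Yes, for genotype-driven sites | No |
| Whole blood before and after infection in one person (Section 11; Table 3 then Table 2) | Removes fixed inherited differences | Yes, given a concurrent uninfected comparison |

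Only the last row supports the word acquired, and section 2.6 does not name it.

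**2. Illustration of size**

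The 0.05 level is from Section 13; two-sided testing is assumed. Group sizes, differences (in SD units) and within-person correlation are all assumptions.

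*Infected versus controls, true infection effect zero, pre-existing difference d.*

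SE = √(1/n₁ + 1/n₀); chance of declaring a difference ≈ Φ(d/SE − 1.96).

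With n₁ = 100, n₀ = 20 and d = 0.5: SE = √(0.01 + 0.05) = 0.245; d/SE = 2.04; Φ(0.08) = 0.53.

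| Infected, controls | d = 0.2 | d = 0.5 | d = 0.8 |
|---|---|---|---|
| 100, 10 | 9% | 33% | 67% |
| 100, 20 | 13% | 53% | 90% |
| 500, 50 | 27% | 92% | about 100% |

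Simulation (5,000 runs, d = 0.5) agrees: 53% for 100 and 20, and 92% for 500 and 50. In the same runs, with correlation 0.7 and no time trend, a paired test of samples before and after infection rejected in 4.9% and 4.4%.

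*Post-infection series alone.* A persistent acquired shift of 0.5 SD, already present at Day 0, was detected by a paired test of Day 0 against a later sample in 4.8% of runs (100 patients). That is the nominal error rate.

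*Power of the contrast recommended below.* This is change in infected against change in uninfected patients, 30 per group, with a true change of 0.5 SD.

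SD of change = √(2(1 − r)); noncentrality = (0.5/SD of change) × √(30/2), with 58 degrees of freedom.

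- r = 0.6: SD of change = 0.894; 0.559 × 3.873 = 2.17; power about 57%.
- r = 0.8: SD of change = 0.632; 0.791 × 3.873 = 3.06; power about 85%.

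A one-group paired test with 30 pairs would show about 84% and 99%, but it assumes no drift over time and is not the contrast that the claim needs.

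**The case against.** The strongest reply is that section 2.6 is a short summary in a sample-handling annex to which the clinical protocol takes precedence. It states no test, adjustment or labelling rule, and the model may sit in an analysis plan not shown. Section 13 foresees multivariable regression, so an unadjusted comparison is not the documented method. The clause on severe disease and clearing points to a contrast among infected patients, with controls perhaps only a reference. The needed blood is also earmarked for this work: Section 11 plans genetic and epigenetic analysis during post-vaccination monitoring and at breakthrough infection.

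Much of this stands. A reader might infer that the plan will label every infected-versus-control difference as acquired, or that it has decided against using pre-infection samples. The documents support neither: section 2.6 says that the two kinds of feature will be told apart, and the rest of the protocol schedules the samples that could help. The rejection rates are also illustrations, since a difference was put in by assumption and an unadjusted test found it.

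What does not fall away is the affirmative claim. Regression adjustment helps only for causes that are measured and modelled. A contrast among infected patients also lacks a pre-infection reference if sampling starts at the first positive test. No later model can recover a pre-infection reference that was never assayed. By contrast, Task 6.9 in the same annex explicitly names longitudinally collected samples for its long-term question; Task 6.7 does not.

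**Conclusion.** The point holds in a limited form. The comparison named in section 2.6 does not support its statement that inherited and infection-acquired features will be separated. Genotype data isolate the inherited part; the remainder, pre-existing or acquired, stays mixed unless a pre-infection sample is used. Such samples are scheduled for some patients, and the claim is not linked to them.

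The logical point needs no numerical assumption. The size does: with 10 to 50 controls and 100 to 500 infected patients, a purely pre-existing difference of 0.5 SD would be declared in 33% to 92% of cases. How large such differences are in these cohorts is not known from the documents. This merits a change to the plan because it concerns a stated conclusion and the remedy uses blood already scheduled. It does not show that the epigenetic work as a whole is badly designed.

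**What to change.** In Annex 4, section 2.6:

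1. Base any conclusion that a feature was acquired through infection on the within-patient change from the last available pre-infection whole-blood sample (Section 11 visit or Annex 4 Table 3) to the post-infection samples of Table 2.
2. Compare that change with the change over similar dates in patients of the same fragile group and vaccination status who stayed uninfected. Without this, a change from before dose 1 to after a breakthrough infection also contains the effects of vaccination and time.
3. Use the sequencing data from Task 6.6 to flag genotype-driven sites.
4. Where no pre-infection sample exists, report the infected-versus-control contrast as association only, and withdraw for it the statement that inherited and acquired features will be differentiated.

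The cost is annex wording and the choice of which stored samples are assayed. The drawback is a smaller paired set of unknown size: some patients enter already infected, vaccine monitoring may start only at month 3 (Section 11), and Level II assessments depend on each cohort's feasibility. At 30 per group, power for a 0.5-SD change at one site, at the 5% level, is only about 57% to 85%. The number of usable pairs should therefore be counted before samples are chosen, with the association wording kept as the fallback.

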2.7 INTESTINAL MICROBIOME PROFILING (TASK 6.8)

This task will profile compositional and functional structures of the microbiome from faecal samples by NGS approaches, in order to elucidate the role of the intestinal microbiome in the susceptibility, progression and severity of COVID-19 infection.

2.8 RESPIRATORY MICROBIOME DYNAMICS (TASK 6.9)

We will investigate differences in the respiratory microbiome composition by combining meta-transcriptomic and metagenomic sequencing to analyse both RNA and DNA viruses and the bacterial and fungal fractions. This will firstly elucidate the role of commensal flora and of co-infecting respiratory pathogens in influencing COVID-19 disease severity. Secondly, long-term carriage and impact of SARS-CoV-2 on the respiratory microbiome will be assessed on longitudinally collected prospective samples (6-12 months post-recovery and new infections).

3. SAMPLE TIMEPOINTS

An overview of sample types to be collected at each time point can be found in Table 1 below. No collection material will be provided within this study, but recommended materials to be used for each collection can be found in the section entitled “Detailed sample collection and storage instructions”.

Table 1. Overview of required biosamples associated analysis within WP6. Task numbers correspond to tasks described in the Description of Work, Amendment 1, Annex 1.

| Sample type | Task | Analysis |
|--------------------------------------|----------|---|
| NP swab | Task 6.2 | Viral variant sequencing |
| | Task 6.9 | Respiratory microbiome analysis |
| Serum | Task 6.3 | Serology |
| | Task 6.6 | Assessment of auto-antibodies against type I IFNs |
| EDTA plasma | Task 6.5 | Cytokine analysis |
| Heparin blood (PBMCs) | Task 6.4 | Cellular immunity characterization |
| EDTA whole blood | Task 6.6 | Human WGS or WES |
| | Task 6.7 | Epigenomics |
| Stool sample (faeces or rectal swab) | Task 6.8 | Intestinal microbiome analysis |

3.1 SAMPLING TIMEPOINTS FOR COVID-19 PATIENTS (INCLUDING REINFECTIONS AND BREAKTHROUGH INFECTIONS IN VACCINATED INDIVIDUALS)

3.1.1 Sample collection and management

Sampling is required to be performed on the day of diagnosis and at following timepoints as shown in Table 2. Patient inclusion will primarily be based on availability of informed consent for the outlined tasks as well as availability of multiple samples per patient. Informed consent forms should clearly request permission to perform human genetic and epigenetic analyses, without which these analyses cannot be undertaken.

Table 2. Overview sampling and data collection in ORCHESTRA cohorts in COVID-19 patients including long-term sequelae.

| | D0 ¹ | 3 months ¹ ±1 month | 6 months ¹ ±1 month | 12 months ¹ ±1 month | 18 months ¹ ±2 month | Objective |
|---|-----------------|-----------------------------------|-----------------------------------|------------------------------------|------------------------------------|--|
| NP swab | x | x ^{2,3} | x ^{2,3} | x ^{2,3} | x ² | Viral variant and metagenomic sequencing |
| 2 x 2 mL serum tube (serum) | x | x | x | x | x | Immune - serology and type I IFNs autoantibodies |
| 4 mL EDTA blood tube (plasma) | x | x ⁴ | x ⁴ | x ⁴ | x ² | Immune - cytokine and chemokine |
| 1 (if possible 2) 9 mL heparin tube (PBMCs) | x | x ⁴ | x ⁴ | x ⁴ | x ² | Immune - cellular |
| 2 x 2 mL EDTA tube (whole blood) | x | x | x | x | x | Genetic and epigenetic analyses |
| Stool sample (faeces or rectal swab) | x | | x | | x | Metagenomic sequencing |

1. Day 0: first positive SARS-CoV-2 PCR test. Follow-up of 3, 6, 12, and 18 months start from Day 0.
2. Reassessed only if outside the normal ranges at the previous assessment or if clinically indicated.
3. At least one of the three timepoints (month 3, month 6, month 12) is required to perform metagenomic analyses.
4. At least one of the three timepoints (month 3, month 6, month 12) is required.

| | |
|----------|--|
| Level I | Assessments of Level I are mandatory |
| Level II | Customized according to the feasibility of each cohort |

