24. Urine tests: pH, concentration, protein, glucose, red blood, white blood cell count
25. CD4 lymphocyte count; HIV-viral load; AIDS status
26. HIV-therapy: drug name and dose (only ongoing treatment); previous switch to other regimens for virological failure
27. Questionnaires to address cognitive status: Cognitive Failure Questionnaire (CFQ), Mini-Mental State Examination, Clinical Dementia rating Scale, Montreal Cognitive Assessment (MOCA).
28. Results of SARS-CoV-2 molecular test on amniotic fluid
29. Weight, height/length, cranial circumference, BMI
30. Type of transplant (heart, lung, kidney, liver, pancreas); single-combined; year of transplantation
31. Graft function: good, impaired, failure, rejection acute-chronic, recurrence of underlying disease, other
32. Immunosuppressive regimen: drug name and dose
33. According to Common Terminology Criteria for Adverse Events (CTCAE)
34. At least one of three timepoints (month 3, month 6, month 12) is required to perform metagenomics analysis.
35. At least one of the three timepoints (month 3, month 6, month 12) is required.

Table 2. Schedule of post-vaccination assessments

| | 1 st dose | 2 nd dose ² | 3 months (± 1 month)* | 6 months (± 2 months)* | 12 months (± 3 months)* |
|--|----------------------|-----------------------------------|--------------------------|---------------------------|----------------------------|
| Baseline information¹ | | | | | |
| Underlying fragile condition | X ¹ | X ¹ | | | |
| Healthcare setting (i.e. LTCF) | X ¹ | X ¹ | | | |
| Comorbidities | X ¹ | X ¹ | | | |
| Concomitant medical treatments | X ¹ | X ¹ | | | |
| Past and/or new COVID-19 disease ³ | X ¹ | X ¹ | X | X | X |
| Clinical evaluation | | | | | |
| Relevant medical new events ⁴ | X | X | X | X | X |
| Clinical symptoms suggestive of COVID-19 | X | X | X | X | X |
| Lab assessment | | | | | |
| Whole blood count | X | X | | | |
| CD4/CD8 count | X | X | | | |
| IgG level | X | X | | | |
| C3 level | X | X | | | |
| Immunology | | | | | |
| Immune - serology and type I IFNs autoantibodies | X | X | X | X | X |
| Immune - cytokine and chemokine | X | X ⁷ | X ⁷ | X ⁷ | X ⁷ |
| Immune - cellular | X | X ⁷ | X ⁷ | X ⁷ | X ⁷ |
| Microbiological tests-NP swabs | | | | | |
| Viral variant and metagenomics sequencing | X ⁵ | X ⁵ | X ⁶ | X ⁶ | X ⁶ |
| EDTA whole blood | | | | | |
| Genetic and epigenetic analysis | X | | X | X | X |
| Stool Sample (faeces or rectal swab) | | | | | |

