10. INCLUSION AND EXCLUSION CRITERIA

Inclusion criteria are:

[figure not shown]
- Any age
- Person (or attorney or deputy who has been authorized to make the decision for patients who lack capacity) consent to participate, or appropriate local waiver of consent.

The only exclusion criteria will be the lack of consent to participate to the study.

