For patients with a past and/or new diagnosis of SARS-CoV2 infection/COVID-19 disease a pre-established long-term follow-up including multiple diagnostic levels in order to adapt to all the participating cohorts is requested. A detailed overview of the schedule of the study visits and the clinical parameters to be recorded is shown in **Table 1**. Patients who have already had COVID, and new patients being diagnosed with COVID, who can be followed up to at least 12 months, and for whom data can be collected according to **Table 1** should be included. In specific fragile cohorts, such as children cohorts, virtual assessments are allowed.

For patients who have been or will be vaccinated against COVID-19 during the study period, a pre-established monitoring of safety and efficacy in terms of immunological response will be performed. A detailed overview of the schedule of the clinical and laboratory parameters to be recorded is shown in **Table 2**. Patients who have already been vaccinated, or will be vaccinated, who can be followed for 12 months, and for whom data can be collected according to Table 2 should be included. The monitoring should start from the days of first and second dose administration when possible (i.e. vaccination administered in the same center where the patient is followed for the fragile condition), alternatively patients will be monitored at 3±1, 6±2 and 12±3 months after the first vaccination dose.

- Vaccination safety will be assessed by a dedicated questionnaire (Annex 3) distributed to patients at baseline or during the first monitoring visit.

- Vaccination efficacy will be established analyzing the immune response at the predefined time-points. The humoral immune response to vaccination will be assessed by a serological assay able to detect anti-Spike and anti-Nucleocapsid antibodies as well as seroneutralization assays in sera samples. The latter will be useful to exclude possible natural infection at the baseline (1st/2nd dose, or first post-vaccination monitoring visit). The cytokine and cell-mediated immune response to vaccination will be assessed in a subgroup of patients by centralizing samples to a referral laboratory, according to local ethic rules and budget. The number of SARS-CoV-2 paucisymptomatic or symptomatic infection despite vaccination will be also assessed by SARS-CoV-2 detection in respiratory/saliva sample.

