12. STUDY VARIABLES

Endpoint variables:

- Infection with SARS-CoV2 detected by RT-PCR on respiratory/saliva specimens;
- Reinfection and/or clinical relapse defined according to recent proposed definitions (7);
- Clinical spectrum of COVID-19 according to WHO mild, moderate, severe, and critical criteria (<https://www.who.int/publications/i/item/WHO-2019-nCoV-clinical-2021-1>);
- Duration of viable viral shedding in fragile patients diagnosed with COVID-19;
- Immune response in patients diagnosed with and/or vaccinated against COVID-19 assessed according to study protocol procedures (see above);
- All-cause mortality during the follow-up period;
- Change in basal clinical condition assessed by questionnaire on functional status and/or according to specific parameters of underlying fragile condition (i.e. graft function, cancer stage etc).

Baseline variables will include:

- Demographic data (sex, date of birth, ethnicity, blood group);
- Underlying conditions;
- Vaccination status against respiratory infectious diseases (i.e. Influenza, pneumococcus, BCG) if available.

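### Annex 4 and Table 1 tie prospective cytokine, cellular and swab-metagenomic work to later samples, which selects on survival and conflicts with the aim of predicting severity and mortality

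*Protocol*

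**What the plan says.** Annex 4 section 3.1.1 asks for sampling on the day of diagnosis and at the later visits of its Table 2. It then sets the selection rule for the laboratory work: "Patient inclusion will primarily be based on availability of informed consent for the outlined tasks as well as availability of multiple samples per patient".

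Table 2 adds conditions by specimen:

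- **Plasma (cytokines) and PBMCs (cellular immunity):** note 4, repeated as footnote 35 of Table 1 in protocol section 3.2, reads "At least one of the three timepoints (month 3, month 6, month 12) is required".
- **Nasopharyngeal swab:** note 3 reads "At least one of the three timepoints (month 3, month 6, month 12) is required to perform metagenomic analyses". Footnote 34 of Table 1 says the same.
- **Serum and whole blood:** neither note applies.

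On timing, Day 0 is the first positive PCR test: "Follow-up of 3, 6, 12, and 18 months start from Day 0". The 3-month visit has a window of ±1 month.

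On the aims, Annex 4 section 2.4 (Task 6.5) states that "panels of cytokine markers predicting disease severity, mortality, breakthrough infections, and long term sequelae will be generated". Section 2.8 (Task 6.9) gives as its first aim the influence of commensal flora and co-infecting pathogens on COVID-19 severity. Protocol section 12 lists "All-cause mortality during the follow-up period" as an endpoint, with no landmark.

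**The concern.** A marker panel meant to predict death or severity should be built in everyone who had the marker measured at the start, whatever happened next. Here the specimen rules ask for something only survivors can supply. If they are used to choose which patients are assayed or analysed, early deaths are removed because of the outcome under study. The question then becomes whether the acute marker predicts death after the qualifying sample, among people who lived to give it.

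Two losses follow. Fewer deaths are available, which costs power. A marker that acts mainly on early death may show no association at all, and enlarging the cohort would not repair that. The Cox and Fine-Gray models in protocol section 13 cannot bring back patients who were never included.

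This is separate from cohort entry. Protocol section 11 already favours patients "who can be followed up to at least 12 months, and for whom data can be collected according to" Table 1. The point here is a second selection, at the laboratory stage, of patients properly enrolled and sampled at diagnosis.

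**Working it through.** The protocol states no sample size, event count or power for these analyses, so there is no figure of its own to reproduce. The check is a reading of the windows, followed by two illustrations on assumed inputs.

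**1. Earliest qualifying later sample.** 3 months − 1 month = month 2 after Day 0. A patient who dies before month 2 cannot meet note 4 / footnote 35 or note 3 / footnote 34, however complete the Day 0 sampling was.

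**2. Rules against aims**

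| Prospective specimen | Later sample | Aim affected |
|---|---|---|
| Plasma | Required (note 4 / footnote 35) | Task 6.5: severity and mortality panels |
| PBMCs | Required (note 4 / footnote 35) | Task 6.4: phenotypes by disease course and severity |
| Nasopharyngeal swab | Condition of metagenomic analysis (note 3 / footnote 34) | Task 6.9: severity |
| Serum, whole blood | No note; only the general selection sentence | Serology, autoantibodies, genetics, epigenetics |

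No section says that patients with only a Day 0 sample stay in when they died, and none restricts the mortality aim to deaths after a landmark.

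**3. Illustration: loss of power.** Assumed, not in the documents: 300 patients with an acute sample, 18-month mortality 20%, hazard ratio 1.5 per SD of the marker throughout, two-sided 0.05 (protocol section 13 gives 0.05 without sidedness).

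Deaths with everyone included: 300 × 0.20 = 60. Deaths kept = 60 × (1 − share before month 2).

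Approximate power = Φ(√D × ln 1.5 − 1.96), with ln 1.5 = 0.405.

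| Share of deaths before month 2 | Deaths kept | √D × 0.405 − 1.96 | Power |
|---|---|---|---|
| none removed | 60 | 1.18 | 88% |
| 50% | 30 | 0.26 | 60% |
| 70% | 18 | −0.24 | 40% |
| 85% | 9 | −0.74 | 23% |

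A simulation of the same setting (piecewise-exponential survival, Cox score test) agrees within two points and gives about 59% in the 50% row.

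The loss depends on the setting. With 500 patients, 20% mortality and half the deaths early, deaths fall from 100 to 50 and power from about 98% to about 81%, a drop of about 17 points.

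**4. Illustration: a marker of early death only.** Assumed: early risk 20% with a high marker and 5% with a low one, and late risk 3% in both groups among those who survive the early period.

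- Everyone included: high 0.20 + 0.80 × 0.03 = 0.224; low 0.05 + 0.95 × 0.03 = 0.0785; risk ratio 0.224 / 0.0785 = 2.85.
- Later sample required: 0.03 / 0.03 = 1.00.

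Under these inputs the signal disappears rather than weakens.

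**The case against.** The strongest reply is that the text sets a collection schedule, not an analysis filter. Several parts of it stand.

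- The selection sentence is qualified by *primarily*, and multiple samples is not defined. Several specimen types from one visit is a possible reading, although the preceding sentence speaks of diagnosis and later visits.
- Note 4 is attached to the follow-up cells and can be read as a relaxation: one later draw is enough instead of three. Unlike note 3, it does not say that analysis depends on it. That defence is not open for the swab.
- WP6 also uses retrospective acute-stage samples (Annex 4, executive summary), which this prospective table does not govern.
- The documents state no null hypothesis or analysis set for the panels, and an analysis plan that is not shown may define the mortality analysis.

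Other parts do not rescue the text. Annex 4 yields to the clinical protocol, but footnotes 34 and 35 are in the clinical protocol. Section 10 says "The only exclusion criteria will be the lack of consent to participate to the study", but that governs entry to the cohort, not laboratory selection. Section 14.4 allows data entry after death, which preserves clinical data but does not supply a month 3 sample. An analysis plan could not recover samples that were never shipped or assayed because of these rules.

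A reader might infer that early deaths do drop out of all WP6 work, so that any mortality panel covers late deaths among survivors only. The documents do not support that. The discretion in the wording, the retrospective samples, and the absence of any note on serum and whole blood all leave room for early deaths to be analysed.

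**Conclusion.** The concern holds in a limited form. Followed as written, the prospective cytokine and cellular rules require a sample that cannot exist before month 2. The swab rule makes such a sample a condition of metagenomic analysis. Applied to the severity and mortality aims of Task 6.5 and the severity aim of Task 6.9, they select on survival and conflict with those aims. For serology and genetics, only the looser selection sentence is at issue.

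The direction follows from the text; the size does not. On the assumed inputs (300 patients, 20% mortality at 18 months, hazard ratio 1.5 per SD), power falls from about 88% to between about 59% and 23% as the early share of deaths runs from 50% to 85%. Weakening of the severity gradient is plausible but was not calculated, and critically ill patients who survive would remain. The wording should be changed, since the rule is stated, it bears on a stated aim, and the change is cheap.

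**What to change.** In Annex 4 section 3.1.1, Table 2 notes 3 and 4, and Table 1 footnotes 34 and 35:

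1. Limit the multiple-sample and month 3/6/12 conditions to longitudinal analyses, such as persistence and long-term sequelae, and say whether multiple means time points or specimen types.
2. State that severity and mortality analyses include every consenting patient with an acute sample, whether or not a later one exists.
3. Where an analysis keeps the later-sample condition, start its clock at that sample and report it as mortality after that sample.

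The cost is a wording change in the annex and two footnotes. Diagnosis samples are already scheduled. The downside is assaying some single-timepoint samples that will not feed the longitudinal analyses.
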